3.1.2 Dose Escalation (Hypofractionation)

Dose hypofractionation escalation will follow the classical ‘3+3’ trial design. If none of the first three patients in a Dose level experiences a dose-limiting toxicity during the DLT period, another three patients will be treated at the next higher Dose level. However, if one of the first three patients experiences a dose-limiting toxicity during the DLT period, three more patients will be treated at the same Dose level. Dose escalation continues until the final Dose level meets safety criteria or at least two patients among a Dose level group of three to six patients experience dose-limiting toxicities (i.e., $\geq 33\%$ of patients with a dose-limiting toxicity at that Dose level).

Dose escalation (**Table 1**) will proceed in parallel in Arm 1 and Arm 2 in Dose level groups of 3–6 patients. The MTD is the dose level at which no more than 1 of up to 6 patients experience DLT during the DLT period, and the dose below that at which at least 2 (of ≤ 6) patients have DLT as a result of treatment.

Dose escalation will follow the rules outlined in the Table below for each Arm (1 or 2) independently as MTD and toxicities are expected to be different as a result of prior treatment.

Number of Patients with DLT at a Given Dose Level	Escalation Decision Rule
0 out of 3	Enter up to 3 patients at the next dose level
≥ 2	Dose escalation will be stopped. This dose level will be declared the maximally administered dose (highest dose administered). Up to three (3) additional patients will be entered at the next lowest dose level if only 3 patients were treated previously at that dose.
1 out of 3	Enter up to 3 more patients at this dose level. 
• If 0 of these 3 patients experience DLT, proceed to the next dose level.• If 1 or more of this group suffer DLT, then dose escalation is stopped, and this dose is declared the maximally administered dose. Up to three (3) additional patients will be entered at the next lowest dose level if only 3 patients were treated previously at that dose.
≤ 1 out of 6 at highest dose level below the maximally administered dose	This is the MTD and is generally the recommended phase 2 dose. 6 additional patients may be entered at the recommended phase 2 dose.

There will be no radiation dose modifications except planned Dose levels.

Abbreviated Title: Image guided radiation

Version Date: 06/03/2024

If a patient did not experience DLT and did not finish treatment, he will not be evaluable for toxicity and will be replaced in the dose level.

If patients develop side effects considered DLT, they will be taken off protocol treatment and may receive additional radiation as needed in standard fractionation to complete the treatment.

3.2 QUESTIONNAIRES (FOR ENGLISH SPEAKING PATIENTS ONLY)

(For English speaking patients only because questionnaires are not validated in other languages.)

Questionnaires will be collected on this trial, typically prior to visiting with the physician at each visit or within 1 week prior at the appropriate time points ([Appendix B](#)). Questionnaires may be completed in paper or electronically, but every effort will be made to have each patient complete questionnaires in the same format.

The timing of collection is noted on the study calendar in section [3.3](#).

The total time anticipated to complete all questionnaires below is 20 minutes.

Once data are abstracted, questionnaires will be maintained in the research chart (print or electronic). If stored, electronically, these files will have restricted access and be accessible only to members of the study team. In the event that questionnaires are stored electronically, paper copies will be shredded.

3.3 STUDY CALENDAR

Procedure	Screening	Baseline ¹	Active RT treatment (2-4 weeks)	Follow Up, Months ⁷		
				1	3	6, 9, 12, 15, 18, 21, 24
RT treatment			X			
Medical History/Records	X					
Confirmation of Pathology	X					
Physical exam, vital signs, ECOG	X	X		X		
CBC with differential and platelet count		X				
Biochemical profile ²		X				
PSA	X	X			X	X ⁵
Testosterone		X			X	X ⁵
HIV	X					
CD4+ T-cell count for HIV positive patients	X					
Lymphocyte phenotype TBNK		X		X	X	X
Adverse Events		X	X	X	X	X
Concomitant Medications		X	X	X	X	X
mpMRI	X					X ⁸
Whole body bone scan or 18F-NaF PET/CT imaging ⁹	X					
CT of the abdomen and pelvis (if clinically indicated)	X					
Blood for correlative studies		X	X ³	X	X	X ⁵
Urine for correlative studies		X	X ³	X	X	X ⁵
Questionnaires ⁶		X				X ⁴
Archival tissue (if available, blocks or sections from prostatectomy or biopsies will be requested)		X				
Contact by phone call, e-mail or other NIH approved remote communication platform every 3 months once off treatment and unable to return for visits				X	X	X

1. Tests done at screening do not need to be repeated on baseline if performed in designated time frame prior to start of treatment
2. Biochemical profile: electrolytes, creatinine, BUN, alkaline phosphatase, ALT, AST, total and direct bilirubin
3. Sampling within 24 hours after the last dose of irradiation.
4. Every 6 months after treatment for 24 months
5. Every 3 months after radiation treatment for 24 months
6. Questionnaires: Expanded Prostate Cancer Index Composite (EPIC-26), SHIM, AUA-SI, PROMIS Depression SF4a, PROMIS Anxiety SF4a, PROMIS Psychological Impact Positive SF 4a, Decision Regret Scale. If the patient receives ADT, before initiation of ADT and within one week before starting radiation if ADT initiated more than one month prior to radiation. For English speaking patients only.
7. +/- 1 week for 1 month visit, +/- 2 weeks for 3 and 6 month visits. +/- 4 weeks for next visits. If subjects are not able or willing to come to NIH to FU visits, they will be followed every three months remotely (by phone call, e-mail for adverse events or other NIH approved remote communication platform), further tumor therapy and lab results. Lab results from outside laboratories are accepted. A clinical evaluation may be completed remotely with a member of the study team to determine if the physical exam, vital signs and ECOG may be omitted. A subject may be referred to a local providers for further assessment at the discretion of the investigator after a remote assessment (e.g., finding that requires clinical assessment/follow up). Subjects may also be referred to their local provider for labs. If biochemical failure per **6.3.1** is identified, the second measurement will be obtained for confirmation, ideally at the NIH Clinical Center. Imaging may be delayed, but will be completed as soon as feasible. Collection of research blood or urine will be omitted or collected in a delayed fashion.
8. Only at the 6 month follow up time point.
9. Scans may be omitted if eligibility can be determined from MRI or other imaging results including 18F-DCFPyL.

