The volumes targeted by irradiation in the post-prostatectomy setting (adjuvant or salvage) are relatively standard and have been arrived at by consensus [9]. In general, the remaining seminal vesicles, if any, and the bed of the prostate are included. In some cases, a portion of the pelvic lymph nodes are included. Most commonly, this region receives a total dose of 66 to 72 Gy in 1.8- 2 Gy fractions, given daily Monday through Friday, over 6-7 weeks. Although these treatments are delivered on an outpatient basis, they are a substantial investment of time and may require time away from work and incur transportation costs.

In general, the use of adjuvant and salvage radiation is well tolerated, however a subset of patients will develop acute (during or within 90 days of radiation) or late (more than 90 days after completion of radiation) toxicity. Two recently published randomized trials provide estimates of toxicity with contemporary irradiation techniques [7, 10]. Grade 2 or higher acute genitourinary toxicity occurs in approximately 14% of patients, whereas Grade 2 or higher acute gastrointestinal toxicity occurs in 21% of patients (acute Grade 3 or higher GU and GI, 2% and 0.5% respectively). Grade 2 or higher late genitourinary toxicity occurs in approximately 25% of patients, whereas Grade 2 or higher late gastrointestinal toxicity occurs in 18% of patients (late Grade 3 or higher GU and GI, 7% and 2% respectively).

Radiation is often combined with androgen deprivation therapy (ADT) in patients with prostate cancer treated with salvage radiation after prostatectomy (detectable PSA). Two recently reported randomized trials of salvage radiation after prostatectomy delivered with or without ADT have shown a benefit in progression free survival or overall survival [7, 10]. These trials demonstrated no increase in bowel or bladder toxicity with the addition of ADT to radiation compared to radiation alone. Based on these results, the use of ADT with radiation is considered appropriate in some, but not all, patients receiving salvage radiation. The use of ADT is dependent of specific tumor and patient characteristics, including age, comorbidity, PSA at the time of radiation, Gleason score, margin status, presence of extra prostatic extension, and patient willingness. We will allow patients to receive ADT on this trial if deemed clinically appropriate,

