8.1.2 Secondary Objectives

- Define the toxicity profile of image guided, hypofractionated, focally dose escalated post-prostatectomy radiation. Assessment of acute toxicities for dose escalation will occur through 3 weeks after radiation.
- Describe the rate of PSA control (biochemical progression free survival, bPFS) at 1 and 2 years after treatment with image guided, hypofractionated, focally dose escalated post-prostatectomy radiation. We hypothesize that the rate of PSA control (bPFS) will compare favorably to the rate obtained with salvage radiation previously published series.
- Describe the effects of image-guided, focally dose escalated prostate bed radiation on patient reported outcomes (SHIM, AUA Symptom Index, EPIC-26). We hypothesize a reduction in quality of life (urinary and gastrointestinal) after radiation that persists for several months but returns to baseline in most patients by 2 years after treatment. We hypothesize that erectile dysfunction will progress without improvement over time.

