8.4.3 Analysis of the Secondary Endpoint(s)

- Define the toxicity profile of image-guided, focally dose escalated prostate bed radiation in patients with a local or regional recurrence of prostate cancer after prostatectomy. All AEs except grade 1 with attribution to protocol treatment will be collected in tabulated way and analyzed.
- The rate of PSA control (biochemical progression free survival, bPFS) will be estimated by the Kaplan-Meier survival analysis and effects of clinical variables on bPFS will be assessed by the Cox proportional hazards model.
- The quality of life scores will be summarized at baseline and for each visit. Linear mixed effects model will be used to model quality of life scores at baseline and during and after treatment in which random intercept and random slope are used to account for patient-specific trajectory of quality of life scores. Changes of quality of life scores during and after treatment will be calculated from the estimated linear mixed effect model. The

similar analytical approach will be performed for depression scores and correlated with quality of life scores.

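### No quality-of-life form is scheduled from the start of radiation until month 6, so the early urinary and bowel decline the plan hypothesises is unobserved; sections 3.3, 8.3 and 8.4.3 disagree on timing, and the time effect is not specified

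*Combined protocol and SAP*

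**What the plan says.** **Hypothesis (section 8.1.2).** For urinary and gastrointestinal scores: "We hypothesize a reduction in quality of life (urinary and gastrointestinal) after radiation that persists for several months". The sentence goes on to expect recovery to baseline in most men by 2 years. Erectile function has a different expected course: "We hypothesize that erectile dysfunction will progress without improvement over time".

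**Schedule (section 3.3).** Section 3.2 leaves timing to the calendar: "The timing of collection is noted on the study calendar in section" 3.3. There the questionnaire row is marked at baseline and in the month 6 to 24 column, with the footnote "Every 6 months after treatment for 24 months". Nothing is marked under active treatment, month 1 or month 3. Footnote 6 can give men on ADT a second form shortly before radiation, but that also precedes treatment. The window is plus or minus "2 weeks for 3 and 6 month visits".

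**Evaluability (section 8.3).** A man counts as evaluable for quality of life if he completed the measures at 3 months.

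**Analysis (section 8.4.3).** Scores are summarised at baseline and at each visit. A linear mixed effects model is also fitted, in which "random intercept and random slope are used to account for patient-specific trajectory of quality of life scores". Changes during and after treatment are calculated from that model. The form of the mean time effect (straight line, visit factor or spline) is not given.

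**The concern.** The hypothesis has two phases, a fall and a recovery, and the schedule leaves out the period in which the fall begins. Section 1.2.1 counts toxicity as acute up to 90 days after radiation, and that whole window lies before the first post-treatment form. Section 1.2.3 calls acute and late toxicity, and their effect on quality of life, an important part of assessing altered fractionation, and names EPIC-26, AUA and SHIM as key measures. For a course shortened to 4, 3 or 2 weeks, the patient's own account of the acute phase would be missing.

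The analysis text seems to assume forms that the calendar does not contain: one at 3 months and at least one during treatment. Separately, if the reported changes come from a model that is linear in time, a fall followed by recovery would be misreported even where the scheduled forms capture part of it.

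**Working it through.** **1. The plan's own figure.** No sample size, power, SD or effect size is given for quality of life. The only stated size is the maximum of 48: 3 dose levels × 6 + 6 expansion = 24 per arm, and 24 × 2 = 48. This reproduces.

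**2. The sections side by side.**

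| Source | Implied forms after the start of radiation |
|---|---|
| 3.3 calendar | Months 6, 12, 18, 24 |
| 8.3 evaluability | Month 3 required |
| 8.4.3 analysis | During and after treatment |

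With the 2-week window, the first form on the calendar falls at about 5.5 to 6.5 months. It meets neither the 3-month rule nor the wish for scores during treatment.

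**3. What the schedule and a straight line would show.** The documents give no dip size, so I assume a mean fall of 10 points, reached by month 1, with linear recovery. The three curves cover several readings of "persists for several months but returns to baseline in most patients by 2 years after treatment". With complete data on a common schedule, a mixed model with a straight-line mean and a random intercept and slope has the same mean line as least squares, so least squares is enough.

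At months 0, 6, 12, 18 and 24 the mean time is 12 and Sxx = 144 + 36 + 0 + 36 + 144 = 360. Worked for curve C:

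- Means 0, −10, −6.67, −3.33, 0; overall mean −20/5 = −4.
- Sxy = (−6)(−10) + (6)(−3.33) = 60 − 20 = 40.
- Slope = 40/360 = 0.111 per month; intercept = −4 − 12 × 0.111 = −5.33.
- Modelled change from 0 to 6 months = 6 × 0.111 = +0.7; from 0 to 24 months = 24 × 0.111 = +2.7.

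| Assumed curve | True means at 0, 6, 12, 18, 24 | Straight line | Change 0–6, true / line | Change 0–24, true / line |
|---|---|---|---|---|
| A: low to month 3, recovered by month 6 | 0, 0, 0, 0, 0 | 0, 0, 0, 0, 0 | 0 / 0 | 0 / 0 |
| B: low to month 3, recovered by month 12 | 0, −6.7, 0, 0, 0 | −2.7, −2.0, −1.3, −0.7, 0 | −6.7 / +0.7 | 0 / +2.7 |
| C: low to month 6, recovered by month 24 | 0, −10, −6.7, −3.3, 0 | −5.3, −4.7, −4.0, −3.3, −2.7 | −10 / +0.7 | 0 / +2.7 |

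Curve A contains a 10-point fall that no scheduled form records, so no model can recover it. In B and C the visit means show the month 6 deficit and the recovery, but the straight line reverses the sign of the early change.

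**4. Early forms without a change of model.** Add months 1 and 3 to curve A. Times 0, 1, 3, 6, 12, 18, 24 have mean 64/7 = 9.14 and Sxx = 1090 − 64²/7 = 504.9. Scores 0, −10, −10, 0, 0, 0, 0 give Sxy = −40 + (64 × 20)/7 = 142.9. The slope is 142.9/504.9 = 0.283 per month, a false rise of 24 × 0.283 = 6.8 points. Both changes are therefore needed.

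**5. Would early forms be informative at this size?** Power of a two-sided 5% paired t test at one visit, with noncentrality (change/SD) × √n, for assumed SDs of change of 10 / 15 / 20:

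| n | 10-point change | 5-point change |
|---|---|---|
| 12 | 0.88 / 0.56 / 0.35 | 0.35 / 0.18 / 0.12 |
| 24 (one arm, maximum) | 1.00 / 0.88 / 0.65 | 0.65 / 0.35 / 0.22 |
| 48 (both arms, maximum) | 1.00 / 0.99 / 0.92 | 0.92 / 0.62 / 0.40 |

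A 10-point early fall could be described usefully in a full arm unless the SD is large. A 5-point fall mostly could not.

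**The case against.** Several points against the concern are sound.

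- **Per-visit summaries.** A reader might infer that the dip and recovery cannot be seen at all. Section 8.4.3 does not support that. Its visit summaries would show a deficit still present at month 6 and its later recovery, and month 24 addresses the 2-year limb directly. Several months does not exclude month 6.
- **The model.** A reader might also infer that a straight line will certainly be fitted. In a linear mixed model, linear means linear in the parameters, and a visit factor for the mean is compatible with the text. The random slope, with changes taken from the model, points towards linear time, but the documented defect is that the time effect is unspecified.
- **Acute safety is recorded elsewhere.** Dose-limiting toxicity is assessed to 3 weeks after treatment, and the calendar lists adverse events during treatment and at months 1 and 3. This only partly fills the gap. Section 6.1 requires only serious, related events to be recorded beyond 30 days, although section 3.1.1 says later toxicities will be followed and scored. Neither source is patient-reported.
- **Published rates.** The Grade 2 or higher acute rates in section 1.2.1 (14% genitourinary, 21% gastrointestinal) come from two published trials of existing treatment. They are not forecasts for this regimen and do not measure the size of the gap.
- **Purpose.** The précis aims at a similar rate of late toxicity, so sampling from 6 to 24 months is defensible for that aim. No quality-of-life comparison between dose levels is planned.
- **Erectile function.** Its expected course is steady worsening, so the dip argument does not cover SHIM.

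These points narrow the concern. They do not supply any patient-reported data between the start of radiation and month 6, and they do not reconcile the calendar with sections 8.3 and 8.4.3.

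**Conclusion.** The point holds for urinary and bowel quality of life in this form: the early course is unobserved, a dip that resolves before month 6 is lost whatever the model, and three sections disagree about when forms are collected.

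Taken literally, the section 8.3 rule is met by no scheduled form. It would go too far to conclude that the sponsor means to exclude every man. The wording suggests that a month-3 form may have been intended, and the documents do not settle which section is in error.

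The model criticism is conditional. If mean time is linear, an assumed 10-point month-6 deficit is reported as +0.7, and a full return to baseline at month 24 as +2.7. If visit is a factor, that error disappears and only the sampling gap remains. The dip size, curve shapes and SDs are assumptions; the schedule and the contradictions are not.

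The consequence is limited to a secondary, descriptive endpoint. Escalation decisions and the MTD do not depend on it. The change is worth making because it is cheap and alters what can be reported.

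**What to change.** 1. Add EPIC-26 and AUA-SI at the end of radiation, month 1 and month 3, electronically where the contact is remote. Month 3 is the minimum needed to match section 8.3. SHIM need not be added on this argument.
2. Reconcile the section 3.3 calendar, the section 8.3 evaluability rule and the section 8.4.3 reference to scores during treatment.
3. State the mean time effect in section 8.4.3: visit as a categorical factor (or a spline), with a patient random effect. Report change from baseline at the early visits for the fall and at month 24 for the recovery.
4. If early forms are not added, or for men already past those contacts, limit the quality-of-life hypothesis and conclusions to month 6 onward. In that case correct the 3-month rule and drop the reference to scores during treatment. Item 3 still applies.

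The cost is modest questionnaire burden and a wording change. Research samples are already due within 24 hours of the last fraction, and contacts already exist at months 1 and 3. The full seven-instrument set is expected to take 20 minutes, and only two instruments would be added.

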3.4 RADIATION THERAPY GUIDELINES

3.4.1 Treatment Planning

A CT simulation will be performed in the radiation oncology branch. The bladder should be comfortably full. Contrast is optional, but discouraged as it may distort anatomy and complicate heterogeneity corrections. If possible, additional imaging will be fused to the planning CT scan (i.e., MRI or other imaging on which tumor was identified).

Treatment planning definitions

GTV: gross tumor volume

CTV: clinical target volume

PTV: planning target volume

Arm 1: prostate bed and tumor boost treatment

- **GTV lesion(s):** image defined tumor
- **PTV lesion(s):** GTV lesion + 3 mm posterior and superior margin and 3-5 mm margin in all other dimensions (inferior, lateral, anterior) on the GTV lesion(s). An expansion of the

PTV to a maximum of 7mm in any direction due to imaging or treatment set up uncertainty may be used at the discretion of the treating radiation oncologist.

- CTV prostate bed: The CTV of the prostate bed will use consensus definitions [9, 41].
- Superiorly: The CTV should extend superiorly from the level of the caudal vas deferens remnant. In some cases, the vas deferens remnant may be difficult to visualize. In the absence of gross disease or seminal vesicle remnants, the superior limit of the CTV should extend at least 2 cm and need not extend more than 3-4 cm above the level of the pubic symphysis. The consensus definition calls for “inclusion of the seminal vesicle remnants, if present, in the CTV if there is pathologic evidence of their involvement. However, inclusion of any seminal vesicle remnants seen is recommended.
- Inferiorly: The CTV should extend inferiorly to > 8-12 mm inferior to vesicourethral anastomosis. With axial CT imaging, the anastomosis can often be seen in the retropubic region as one slice below the most inferior urine-containing image (the bladder must be modestly full). Inferiorly, the border of the CTV should be at least 8-12 mm below the VUA. If visualization of the VUA is problematic due to image quality or surgical clip artifacts, the inferior limit of the CTV can extend to a level just above the penile bulb.
- Anteriorly: Below the superior border of the pubic symphysis, the anterior border is at the posterior aspect of the pubis. The CTV extends posteriorly to the rectum where it may be concave at the level of the VUA. At this level the lateral border extends to the levator ani. Above the pubic symphysis the anterior border should encompass the posterior 1-2 cm of the bladder wall at the minimum and posteriorly it is bounded by the mesorectal fascia. At this level the lateral border is the sacrorectogenitopubic fascia or the obturator internus muscle.
- Posteriorly: The CTV extends posteriorly to the anterior rectal wall, but may be somewhat concave around the anterior-lateral aspect of the rectum to adequately encompass the prostate bed.
- PTV prostate bed: 7 mm margin on the prostate bed CTV. A 5-6 mm margin posteriorly may be used if necessary to meet dose constraints.

Arm 2. Prostate bed

- CTV prostate bed: As above
- PTV prostate bed: As above
- Dose to the PTV will be escalated as defined in Section 3.1.2.

